Version 3.0 implements changes requested by the UK Medicines and Healthcare products Regulatory Agency (MHRA) and the German Federal Institute for Drugs and Medical Devices (BfArM). In response to MHRA feedback the following changes have been made: Section 5.1: Inclusion criterion #12: Male patients should use a condom and spermicide (or sexual abstinence*) to prevent pregnancy and drug exposure of a partner, regardless of the gender or childbearing potential of the partner from the day of the first administration of the IP until 3 months after the last administration of the IP. In addition to a condom with spermicide, a second highly effective method of contraception (oral, intravaginal or transdermal hormonal contraceptives, intrauterine device, or intrauterine hormone-releasing system, or sexual abstinence until 3 months after the last administration of the IP) should be used with female partners of childbearing potential. Double barrier methods (a combination of male condom with either a cap, diaphragm or sponge with spermicide) are not considered to be highly effective methods of contraception. Male patients with a pregnant partner should use a condom and spermicide or sexual abstinence* . *True abstinence: When this is in line with the preferred and usual lifestyle of the subject. (periodic abstinence [eg, calendar, ovulation, symptothermal, post-ovulation methods],

declaration of abstinence for the duration of a trial, and withdrawal are not acceptable methods of contraception).

Section 6.3 Measures to minimise bias: randomisation and blinding:

The IVRS/IWRS will be programmed with blind-breaking instructions. ~~The blind may be broken if, in the opinion of the Investigator, it is in the patient's best interest for the Investigator to know the study treatment assignment. The Sponsor must be notified before the blind is broken unless identification of the study treatment is required for a medical emergency in which the knowledge of the specific blinded study treatment will affect the immediate management of the patient's condition (eg, antidote available).~~ In case of an emergency, the Investigator has the sole responsibility for determining if unblinding of a patient's treatment assignment is warranted. Patient safety must always be the first consideration in making such a determination. If the Investigator decides that unblinding is warranted, the Investigator is asked to contact the Sponsor prior to unblinding a patient's treatment assignment unless this could delay emergency treatment of the patient.

In response to BfArM feedback the following change has been made:

Section 5.2: Exclusion criteria:

12. Patient with a heart rate <50 or >120 ~~>100~~ beats per minute (bpm).
13. Patient has clinically significant uncontrolled hypertension (~~>180~~ >160 mmHg) as assessed by the Investigator.

Section 7.3: Withdrawal from the study

When a patient does not meet all the eligibility criteria but is randomised in error, or incorrectly started on treatment, the Investigator should inform the AstraZeneca Study Physician immediately, and a discussion should occur between the AstraZeneca Study Physician and the Investigator ~~regarding whether to continue or discontinue the patient from treatment.~~ Any patient that has been initiated on treatment and subsequently found not to meet all the eligibility criteria must stop the treatment and be excluded from the study. The AstraZeneca Study Physician must ensure all decisions are appropriately documented.

Version 4.0, 11 December 2018
Changes to the protocol are summarised below.

Heart Rate for pre-dose time points on visits 4, 7 and 10 will be taken from Vital Signs.

As per protocol there is no pre-dose ECG for visits 4, 7 and 10.

ECGs will be done as single measurements and not as triplicates.

8.2.4 Electrocardiogram: Triple 12-lead ECG will be obtained as specified in the SoA (Table 1) using an ECG machine that automatically calculates the heart rate and measures

PR, QRS, QT, and QTc intervals. Table 1 does not specify any triplicate ECG time points and therefore the section on triplicate ECG measurement is also irrelevant. Single measurement has been confirmed by sponsor.

ECGs and Vital signs will be measured after 5min rest in a supine position (as flat as possible and what is comfortable for the patient) to ensure consistency between measurements.

Use of supine position (**as flat as possible and what is comfortable for the patient**) for the ECG and vital signs. The same position should be used for all time-points.

Vital Signs will be done as single measurement and not as triplicates.

8.2.3 Vital signs: Vital signs will be measured in a supine position after 5 min rest and will include temperature, SBP and diastolic blood pressure (DBP). Three readings of BP will be taken. The first reading should be rejected. The second and third readings should be averaged to give the measurement to be recorded in the eCRF.

Clinical Stability Check will be done at Screening and before the start of each period.

This is to confirm that stability check will be done before the start of each treatment period.

Drugs of abuse and Alcohol

Screening results for Drugs of abuse and Alcohol will be used to determine Exclusion criterion #21 prior to randomisation due to the logistical accessibility of the results.

Cough Monitoring for Visits 5, 8 and 11 will start on Day 14, just before dosing at site, for 24hours recording

The recording for Visits 3, 6 and 9 are home recordings and will start at least 24 hours before the dosing and will finish pre-dose. Table 1, footnote r. Cough monitoring for Visits 5, 8, and 11 will start on Day 14, just before, for 24 hours recording.

Table 8: “Laboratory safety variables” in section 8.2.1

Clinical safety laboratory assessments of the protocol the following parameters were omitted in the table by error: aPTT=Activated partial thromboplastin time, INR=International normalised ratio; PTT=Partial thromboplastin time.

These parameters are only mentioned in the footnote but will be considered as part of the lab analysis in the table.

This Clinical Study Protocol has been subject to a peer review according to AstraZeneca Standard procedures. The Clinical Study Protocol is publicly registered, and the results are disclosed and/or published according to the AstraZeneca Global Policy on Bioethics and in compliance with prevailing laws and regulations.

TABLE OF CONTENTS

1.	PROTOCOL SUMMARY	10

1. PROTOCOL SUMMARY

1.1 Schedule of Activities (SoA)

Table 1 Schedule of Assessments

	Screening		Treatment periods (Period 1-Period 3)									Follow-up or Discontinuation	Details in CSP section or Appendix
			Period 1			Period 2			Period 3				
Visit	1 ^a	2 ^a	3 ^{b,d}	4 ^c	5 ^b	6 ^{b,d}	7 ^c	8 ^b	9 ^{b,d}	10 ^c	11 ^b	42 days after Visit 11 (or last IP admin)	
Day	-28 to -14	-28 to -14	1	8	14	1	8	14	1	8	14		
Informed consent	X												Section 5.1
Inclusion/exclusion criteria	X	X	X ^e										Section 5.1 and 5.2
Routine clinical procedures													
Demography	X												Section 5.1
Smoking history	X												Section 5.1
Physical examination ^f	X		X		X	X		X	X		X	X	Section 5.1
Medical/surgical history	X												Section 5.1
Vital signs (BP) ^g	X		X	X	X	X	X	X	X	X	X	X	Section 8.2.3
Height	X												Section 8.2.2
Weight	X											X	Section 8.2.2
12-lead ECG ^h	X		X	X	X	X	X	X	X	X	X	X	Section 8.2.4
Previous and concomitant medication	X	X	At every visit and may be conducted by phone if not tied to a visit										Section 6.5
Routine safety measurements													
Adverse events and COPD exacerbations	X	X	At every visit and may be conducted by phone if not tied to a visit									X	Section 8.3
Pregnancy test (urine)	X ^w		X			X			X			X	Section 5.1
Drugs of abuse and alcohol screen ⁱ	X		X			X			X				Section 5.1
Safety laboratory assessments (clinical chemistry, haematology and urinalysis) ^j	X		X		X	X		X	X		X	X	Section 8.2.1

Table 1 Schedule of Assessments

	Screening		Treatment periods (Period 1-Period 3)									Follow-up or Discontinuation	Details in CSP section or Appendix
			Period 1			Period 2			Period 3				
Visit	1 ^a	2 ^a	3 ^{b,d}	4 ^c	5 ^b	6 ^{b,d}	7 ^c	8 ^b	9 ^{b,d}	10 ^c	11 ^b	42 days after Visit 11 (or last IP admin)	
Day	-28 to -14	-28 to -14	1	8	14	1	8	14	1	8	14		
i-STAT measurement ^k			X		X	X		X	X		X		Section 8.2.1
CCI													
CCI													
Pharmacokinetic measurements^m													
Pre-dose PK blood sample			X	X	X	X	X	X	X	X	X		Section 8.5
30 min post-dose PK blood sample			X		X	X		X	X		X		Section 8.5
1 hour post-dose PK blood sample			X	X	X	X	X	X	X	X	X		Section 8.5
2 hours post-dose PK blood sample			X		X	X		X	X		X		Section 8.5
4 hours post-dose PK blood sample			X		X	X		X	X		X		Section 8.5
6 hours post-dose PK blood sample			X		X	X		X	X		X		Section 8.5
8 hours post-dose PK blood sample			X		X	X		X	X		X		Section 8.5
12 hours post-dose PK blood sample			X		X	X		X	X		X		Section 8.5
24 hours post-dose PK blood sample			X		X	X		X	X		X		Section 8.5
Efficacy measurements													
Reversibility testing ⁿ		X											Section 8.1.3
Clinical stability check		X	X			X			X				Section 8.1.2
FEV ₁ stability check ^o						X			X				Section 8.1.2
Spirometry ^p		X	X	X	X	X	X	X	X	X	X		Section 8.1.1
BCSS questionnaire		X	X	X	X	X	X	X	X	X	X		Section 8.1.1

Table 1 Schedule of Assessments

	Screening		Treatment periods (Period 1-Period 3)									Follow-up or Discontinuation	Details in CSP section or Appendix
			Period 1			Period 2			Period 3				
Visit	1 ^a	2 ^a	3 ^{b,d}	4 ^c	5 ^b	6 ^{b,d}	7 ^c	8 ^b	9 ^{b,d}	10 ^c	11 ^b	42 days after Visit 11 (or last IP admin)	
Day	-28 to -14	-28 to -14	1	8	14	1	8	14	1	8	14		
COPD assessment test (CAT)		X	X	X	X	X	X	X	X	X	X		Section 8.1.1
Cough VAS ^q			X	X	X	X	X	X	X	X	X		Section 8.1.1
Cough monitoring ^r			X		X	X		X	X		X		Section 8.1.1
Study treatment administration													
Ipratropium dispensed ^s		X			X			X			X		
Salbutamol dispensed		X	X	X	X	X	X	X	X	X	X		
Randomisation			X										Section 6.3
Inhaler training ^t			X			X			X				
Study treatment kit dispensed (daily dosing) ^u			X			X			X				
Dispense/Check e-Diary/paper diaries ^v		X	X	X	X	X	X	X	X	X	X		

AE=Adverse event; BCSS=Breathlessness, Cough, Sputum Scale; BP=Blood Pressure; COPD= Chronic Obstructive Pulmonary Disease; CSP=Clinical Study Protocol; ECG=Electrocardiogram; e-Diary= Electronic Diary; **CCI** FEV₁=Forced Expiratory Volume in 1 second; IP=Investigational Product; PK=Pharmacokinetics; **CCI**.

- a. All the Screening assessments can be performed at Visit 1 or Visit 2, based on the site’s preference, except for the following:
 - (i) Informed Consent Form (ICF) must be completed at Visit 1 before any study-specific assessments are performed.
 - (ii) Reversibility test with salbutamol and spirometry (to confirm inclusion criterion #6) must be performed at Visit 2 after wash-out is completed. Visit 1 and Visit 2 could be performed on the same day if no wash-out of prior medication is required and the patient visits the site in fasting condition. In case any wash-out of prior medication is required, then Visit 2 will be performed after the wash-out is complete.
- b. Visits 3, 6 and 9 and Visits 5, 8 and 11 will be overnight stay visits; 6 overnight visits are required per patient.
- c. Visits 4, 7 and 10 will be outpatient visits with duration of approximately of 5 hours.
- d. Interval between randomised treatment periods (wash-out period) will be 42 to 49 days (from the last IP administration).

- e. Eligibility for study inclusion will be assessed from Screening Visit data for exclusion criterion #17.
- f. Physical examination will be a complete examination at Screening and at the Follow-up Visit. Brief physical examinations will be performed pre-dose at Visits 3, 6, 9, and 24 hours post-dose at Visits 5, 8 and 11.
- g. Vital signs: Blood pressure will be assessed pre-dose and 1, 2, 4, and 24 hours post-dose at Visits 3, 5, 6, 8, 9 and 11. On Visits 4, 7 and 10 blood pressure will be measured at pre-dose, 1 and 4 hours post-dose. Body temperature will be measured at Screening and at the Follow-up Visit. Heart rate will be assessed by ECG (except pre-dose on Visits 4, 7 and 10, which will be taken from Vital Signs).
- h. 12-Lead ECG measurements will be done pre-dose and 1, 2, 4, and 24 hours post-dose on Visits 3, 5, 6, 8, 9 and 11. At Visits 4, 7 and 10 ECG measurements will be done at 1 and 4 hours post-dose. ECG should be performed before spirometry.
- i. The alcohol screen may be performed using a urine sample or a breath test. Screening results for drugs of abuse will be used to determine exclusion criterion #21 prior to randomisation due to the logistical accessibility of the results.
- j. Safety laboratory tests will be done at Visit 1, pre-dose at Visits 3, 6, 9 and at 24 hours post-dose at Visits 5, 8, 11 and at Follow-up Visit. Safety laboratory tests will be done after 8 hours of fasting. Serology parameters will be measured at Visit 1 only.
- k. i-STAT for glucose and potassium measurements will be done pre-dose and 1, 2, 4 and 24 hours post-dose on Visits 3, 5, 6, 8, 9 and 11. i-STAT will be done after at least 4 hours of fasting.
- █
- m. PK blood samples will be collected from patients who will have specifically consented to the PK assessments at pre-dose and at 30 minutes (min), 1, 2, 4, 6, 8, 12, and 24 hours post-dose at Visits 3, 5, 6, 8, 9 and 11. At Visits 4, 7 and 10 measurements will be done pre-dose and 1 hour post-dose.
- n. Reversibility test includes a pre-salbutamol spirometry and then at 20-30 min post-salbutamol.
- o. FEV₁ stability will be done at Visits 6 and 9 based on the pre-best test review (BTR).
- p. Spirometry measurements will be done at -1 h and -15 min pre-dose and then 15 min, 30 min, 1, 2, 4, 8, 12, 23, and 23:45 hours post-dose on Visits 3, 5, 6, 8, 9 and 11. At Visits 4, 7 and 10 spirometry measurements will be done at -1 h and -15 min pre-dose and at 15, 30 min, 1, 2, and 4 hours post-dose.
- q. Cough VAS will be done pre-dose at Visits 3, 4, 6, 7, 9, and 10, and 24 hours post-dose at Visits 5, 8, and 11.
- r. Cough monitoring will be done starting 24 hours prior to dosing on Visits 3, 6, and 9, and pre-dose at Visits 5, 8, and 11. The recording for Visits 3, 6 and 9 are home recordings and will start at least 24 hours before the dosing and will finish pre-dose. Cough monitoring for Visits 5, 8 and 11 will start on Day 14, just before dosing at site, and will finish 24 hours later. Patients may attend the site between visits to collect the cough monitor prior to the recording start.
- s. All patients will receive ipratropium (20 µg × 2 puffs 4 times per day) during the run-in and wash-out periods. In addition, those patients that were taking any LAMA and/or LABA will be maintained with ipratropium between Visit 1 and Visit 2. Ipratropium should be held at least 8 hours before Visits 3, 6 and 9 (before any pulmonary function test) and during all treatment periods (until last pulmonary function test at Visits 5, 8 and 11).
- t. Inhaler training will be done before starting IP treatment on Day 1 at each treatment period.
- u. The first dose of IP is to be taken at the clinic at 9:00 AM±2 hours on Day 1 of each treatment period (Visits 3, 6 and 9) after the pre-dose specified procedures (and randomisation for Visit 3). On subsequent days of each treatment period, IP is to be taken within ±1 hour of dosing time of Day 1 (and between 7 AM and 11 AM). IP administration will be at the site on Day 1, 2, 8 and 14 of each treatment period. This will be supervised at the clinic. Day 3 to Day 7 and Day 9 to Day 13 of each treatment period - doses will be taken at home.

- v. E-Diary will be used to collect daily BCSS and daily use of rescue medication (salbutamol 100 µg as needed) during the run-in and treatment periods. E-Diary will be used to collect CAT once at screening and daily during treatment periods. In addition, during treatment period daily IP intake will be recorded in the e-Diary. Paper diary will be used to collect AEs and concomitant medication during run-in and wash-out periods. Paper diary is also used to collect rescue medication intake during the wash-out phase.
- w. Pregnancy results at Screening will be used to check the eligibility of the patient for participation in the study.

Note: For assessments occurring at the same time points, the recommended order of assessments is as follows: 1. ECG; 2. Vital signs; 3. i-STAT; 4. PK; and 5. Spirometry (on the actual time points).

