Approximately 145 patients will be screened in order to randomise 72 patients into the study (previous studies estimate the screening failure rate to be approximately 50%). Screening failures are defined as patients who signed the informed consent form (ICF) to participate in the clinical trial but are not subsequently randomly assigned to study treatment. It is anticipated that 54 patients will be evaluable (study completers) assuming an approximate 25% dropout rate. A subset of 36 patients, who will have specifically consented for pharmacokinetics (PK), will undergo PK assessments.

Treatments and treatment duration:

The entire study period is scheduled to take from a minimum of 6.5 months (182 days) to a maximum of 7.5 months (217 days) for each individual patient.

Screening period: This will last up to 28 days and consists of 2 Screening visits (Visit 1 and Visit 2) and a run-in period.

Patients will be requested to stop their usual COPD therapy after signing the ICF at Visit 1 and will be maintained on a mono-component inhaled corticosteroid (ICS) therapy, if required. Patients that were taking any LAMA and/or LABA will be maintained with ipratropium (20 µg × 2 puffs 4 times per day) between Visit 1 and Visit 2. In addition, salbutamol 100 µg will be provided as rescue medication during the study as needed (rescue medication has to be discontinued 6 hours before any pulmonary function test). Visit 1 and Visit 2 could be performed on the same day if no wash-out of prior medication is required and the patient visits the site in fasting condition. In case any wash-out of prior medication is required, then Visit 2 will be performed after the wash-out is complete.

All the screening assessments can be performed at Visit 1 or Visit 2, based on the site's preference, except for the following:

- ICF: This must be completed at Visit 1 before any study-specific assessments are performed.
- Reversibility test with salbutamol and spirometry (to confirm inclusion criterion #6); this must be performed at Visit 2 due to wash-out requirements.

If the forced expiratory volume in 1 second (FEV₁) predicted value is fulfilled according to inclusion criteria, the patient will be started on run-in period to assess clinical stability. If the FEV₁ predicted value is not met, pulmonary function tests could be rescheduled at the latest, up to Day -14.

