4. STUDY DESIGN

4.1 Overall design

This is a randomised, placebo-controlled, double-blind, 3-way complete crossover William's design, international, multi-centre Phase IIa multiple dose study of 1 dose level of AZD8871, an active comparator (Anoro[®] Ellipta[®]) and placebo administered by DPI devices. Approximately 72 eligible male and non-childbearing female patients with moderate to severe COPD before randomisation and fulfilling all of the eligibility criteria will be randomised in a 1:1:1:1:1:1 to 1 of 6 treatment sequences. The study includes 12 visits and the entire study period is scheduled to take from a minimum of 6.5 months (182 days) to a maximum of 7.5 months (217 days) for each individual patient. The aim is to ensure at least 54 patients complete the study.

A subset of 36 patients, who will have specifically consented for pharmacokinetics (PK), will undergo PK assessments.

The study will be conducted at approximately 5 sites in Germany and the UK. Estimated study duration is 12 months.

The study will consist of a Screening period, 3 treatment periods (each separated by a wash-out period), and a Follow-up Visit, as described below.

Screening period: This will last up to 28 days and consists of 2 Screening visits (Visit 1 and Visit 2) and a run-in period.

Patients will be requested to stop their usual COPD therapy after signing the ICF at Visit 1 and will be maintained on a mono-component ICS therapy, if required. Patients that were taking any LAMA will be maintained with ipratropium (20 µg × 2 puffs 4 times per day) between Visit 1 and Visit 2. In addition, salbutamol 100 µg will be provided as rescue medication during the study as needed (rescue medication has to be discontinued 6 hours before any pulmonary function test). Visit 1 and Visit 2 could be performed on the same day if no wash-out of prior medication is required and the patient visits the site in fasting

condition. In case any wash-out of prior medication is required, then Visit 2 will be performed after the wash-out is complete.

All the screening assessments can be performed at Visit 1 or Visit 2, based on the site's preference, except for the following:

- ICF: This must be completed at Visit 1 before any study-specific assessments are performed.
- Reversibility test with salbutamol and spirometry (to confirm inclusion criterion #6); this must be performed at Visit 2 due to wash-out requirements.

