5.1 Inclusion criteria

Patients are eligible to be included in the study only if all of the following inclusion criteria and none of the exclusion criteria apply:

Informed consent

1. Provision of signed and dated, written ICF prior to any study-specific procedures, sampling, and analyses.

The ICF process is described in Appendix A 3.

Age

2. Patient must be 40 to 85 years of age (both inclusive) at the time of signing the ICF (Screening; Visit 1).

Type of patient and disease characteristics

3. COPD Diagnosis: Patient with an established clinical history of moderate to severe COPD for more than 1 year at Screening, according to the GOLD COPD guidelines.
4. Tobacco Use: Patient is a current or former smoker with a history of ≥ 10 pack-years of cigarette smoking [Number of pack-years=(number of cigarettes per day/20)* number of years smoked (eg, 1 pack-year=20 cigarettes smoked per day for 1 year)]. A former smoker is defined as one who has stopped smoking for at least 6 months prior to Screening.
 - Patient smoking other tobacco types (including e-cigarettes) will not be allowed, unless he/she meets the cigarette criterion as well.
5. Patient with post-bronchodilator FEV₁/forced vital capacity (FVC) ratio <70% based on the value reached after inhalation of salbutamol (400 µg) at Visit 2. If criterion is not met, the test can be repeated at the latest, up to Day -14.

6. Patient with post-bronchodilator FEV₁ that must be $\geq 40\%$ and $< 80\%$ predicted normal value at Visit 2. If the criterion is not met, the test can be repeated at the latest, up to Day -14.
7. Patient is willing and, in the opinion of the Investigator, able to change current COPD therapy as required by the protocol and willing to use ipratropium following the approved dosage and regimen (during run-in and wash-out periods) with or without ICS for maintenance therapy of COPD and rescue medication salbutamol (as needed) from Visit 1 to Visit 11.
8. Patient must be able to read, speak and understand local language, and be willing to remain at the study centre as required per-protocol to complete all visit assessments.

Weight

9. Body mass index (BMI) $< 40 \text{ kg/m}^2$ at the time of Screening.

Sex

10. Male and/or females of non-childbearing potential who are not pregnant or lactating.

Reproduction

11. Female patients must be of non-childbearing potential defined as:

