Ipratropium 20 µg × 2 puffs 4 times per day	Mandatory during run-in and wash-out periods but should be held at least 8 hours before Visits 3, 6 and 9 (before any pulmonary function test) and during all treatment periods (until last pulmonary function test at Visits 5, 8 and 11)

ICS=Inhaled corticosteroid.

Table 6 Prohibited medications

Drug Class	Restrictions
ANTICHOLINERGICS	
Oral or parenteral	Wash-out of 72 hours required before Visit 2
Inhaled short-acting, SAMAs	Wash-out of 8 hours required before Visit 2
Inhaled long-acting, LAMAs	Wash-out of 72 hours before Visit 2
B₂-ADRENERGIC AGONISTS	
Inhaled short-acting, SABAs (except Salbutamol rescue medication)	Wash-out of 6 hours before starting first pulmonary function test at each study visit
Inhaled long-acting, LABAs (BID or QD)	BID: Wash-out of 48 hours required before Visit 2
	QD: Wash-out of 7 days required before Visit 2
Oral short-acting	Wash-out of 24 hours required before Visit 2
COMBINATIONS (INHALED)	
Inhaled long-acting LABA/LAMA combinations (BID or QD)	BID: Wash-out of 48 hours required before Visit 2
	QD: Wash-out of 7 days required before Visit 2
LABA + ICS fixed-dose combinations	Stop combination at least 48 hours before Visit 2 and switch to ICS mono-component at Visit 1

Table 6 Prohibited medications

Drug Class	Restrictions
SABA + anticholinergic agent	Wash-out of 72 hours required before Visit 2
CORTICOSTEROIDS	
Continuous oral or parenteral	Wash-out of 6 weeks required before Visit 2
OTHERS	
Methyl-xanthines	Patients with these medications should not be enrolled into the study
Mast cell stabilisers	Wash-out of 5 days required before Visit 2
Leukotriene modifiers	Wash-out of 48 hours required before Visit 2
Selective and non-selective β -blocking agents (oral or topical including eye drops)	Patients with these medication should not be enrolled into the study
Phosphodiesterase IV inhibitors	Wash-out of 4 weeks required before Visit 2
Anti-IgE and anti-IL-5 antibody therapies	Wash-out of 6 months required before Visit 2
Medications that prolong the QT/QTc interval (other than inhaled β_2 agonist) eg, anti-arrhythmics, anti-psychotics and fluoroquinolones	Stable at least 4 weeks prior to Visit 2
“Experimental”, non-approved medications	Wash-out of 3 months before Visit 1
Strong inhibitors of carboxyl esterase 2	Wash-out of 5 days required before Visit 2
Live attenuated vaccine	Wash-out of 30 days before screening

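### The protocol contradicts itself on bronchodilator cover between Visits 1 and 2: Table 1 schedules no ipratropium or salbutamol dispensing before Visit 2, and Section 4.1 names a narrower group for ipratropium than four other places do

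*Protocol*

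**What the plan says.** **When usual therapy stops.** Protocol Section 4.1: "Patients will be requested to stop their usual COPD therapy after signing the ICF at Visit 1". The synopsis, Section 6.5 and SAP 1.2 agree.

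**When study supplies are dispensed.** In Table 1 (Section 1.1) the row "Ipratropium dispensed" is marked at Visits 2, 5, 8 and 11. The row "Salbutamol dispensed" is marked at every visit from 2 to 11. The Visit 1 cell is empty in both.

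**Who takes ipratropium between Visits 1 and 2.** Footnote s to Table 1: "those patients that were taking any LAMA and/or LABA will be maintained with ipratropium between Visit 1 and Visit 2". The synopsis: "Patients that were taking any LAMA and/or LABA will be maintained with ipratropium". Section 2.3 and SAP 1.2 name the same group. Section 4.1 reads instead: "Patients that were taking any LAMA will be maintained with ipratropium".

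**When salbutamol is in use.** Inclusion criterion 7 (Section 5.1) requires willingness to use "rescue medication salbutamol (as needed) from Visit 1 to Visit 11". Section 6.5 has it supplied throughout the study.

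**Other text on ipratropium.** Section 6.5 and Table 5 place it in the run-in and wash-out periods. Section 4.1 counts run-in from Visit 2 to Visit 3.

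**The concern.** Section 2.3 presents ipratropium and salbutamol as measures that limit the risk to patients who must give up their usual treatment. That risk begins at Visit 1, and the dispensing rows begin at Visit 2. For a patient who needs a wash-out the two visits cannot fall on the same day, so there is an interval in which the text expects study medication to be in use and the schedule provides no point at which to hand it out.

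The second conflict concerns who is covered. A site working from Section 4.1, the full design description, finds no ipratropium provision for a former LABA-only user. A site working from the synopsis, Section 2.3 or footnote s does. Similar patients could then be managed differently according to which page the site opens. At stake are patient cover during screening and consistent conduct across sites.

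**Working it through.** The plan states no figure on this point, so the check is a comparison of passages plus the minimum intervals implied by Table 6.

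**Step 1: column check.** The first mark in both dispensing rows sits in the second screening column. The reversibility-testing mark is in the same column, and footnote a fixes that test to Visit 2. The first scheduled dispensing is therefore Visit 2.

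**Step 2: dispensing against stated use.**

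| Drug | Stated use before Visit 2 | First dispensing mark | Footnote on the row covering Visits 1 to 2 |
|---|---|---|---|
| Ipratropium | Yes, for former LAMA and/or LABA users (footnote s, synopsis, Section 2.3, SAP 1.2) | Visit 2 | Yes: footnote s states use but names no supply point |
| Salbutamol | Yes, from Visit 1 (inclusion 7) and throughout the study (Section 6.5) | Visit 2 | None |

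The supply text in Section 6.5 and Table 5 does not fill the ipratropium gap. It covers run-in and wash-out, and run-in starts at Visit 2.

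**Step 3: who is covered.** Four places (footnote s, synopsis, Section 2.3, SAP 1.2) say LAMA and/or LABA. One place (Section 4.1) says LAMA. The difference is the former LABA-only user.

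**Step 4: length of the interval.** Visits 1 and 2 may share a day only if no wash-out is needed. Table 6 gives these wash-outs before Visit 2:

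- twice-daily LABA or LABA/LAMA: 48 hours (2 days);
- LAMA: 72 hours (3 days);
- once-daily LABA or LABA/LAMA: "QD: Wash-out of 7 days required before Visit 2".

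If the last dose of the old drug is taken at Visit 1, these are the shortest times from Visit 1 to the first dispensing mark. Table 1 places both visits in Day -28 to Day -14, so the longest is 28 − 14 = 14 days.

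**Step 5: effect on the statistics.** Neither the Section 9.2 sample size nor the primary mixed model uses anything from the Visit 1 to 2 interval. The Visit 2 pre-bronchodilator FEV₁ replaces a period baseline only when both Day 1 pre-dose values are missing.

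**The case against.** The strongest reply is that Table 1 must be read with its footnotes. Footnote s is attached to the ipratropium row and requires cover between the visits, so a site following the whole table would supply it. Footnote a also lets screening activities move between Visits 1 and 2, and dispensing is not among its exceptions. Section 8 asks for adherence to the design requirements, including the schedule; it does not rank the grid above the text. Section 6.5.3 allows rescue medication at any time in the study. Section 4.1 does not say that only LAMA users are covered, and four places against one suggests a drafting omission.

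Much of this stands, and it rules out several stronger inferences:

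- **That following Table 1 sends patients home with no bronchodilator for 7 days or more.** The figures in Step 4 are wash-out lengths. They become a gap in study-supplied cover only if a site overlooks footnote s, inclusion 7 and Sections 2.3 and 6.5. Even then, Table 6 can be read as leaving patients' own short-acting inhalers usable until 6 to 8 hours before testing.
- **That Visit 2 spirometry or eligibility is distorted.** Ipratropium is withheld 8 hours and salbutamol 6 hours before lung-function tests, and the FEV₁ and FEV₁/FVC entry criteria use post-salbutamol values. An effect is speculative.
- **That treatment comparisons are biased.** The interval precedes randomisation.
- **That Section 4.1 forbids ipratropium to LABA users.** It omits them; it does not exclude them.

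The reply does not remove the contradiction. Footnote s states use without scheduling supply. The salbutamol row has no equivalent note. Footnote a speaks of assessments and does not mention dispensing. Same-day visits are closed to exactly the patients who need a wash-out.

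**Conclusion.** The point holds as an internal contradiction in the current text, in two parts: the dispensing rows start one visit later than the stated use of both drugs, and Section 4.1 names a narrower group for ipratropium than the other four places. It is more than clerical, because this cover is a stated risk-limiting measure and literal readings of different sections lead to different handling of LABA-only users.

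A literal reading of the grid or of Section 4.1 could leave some patients without study-supplied cover for at least 48 hours, 72 hours or 7 days, assuming that the old therapy stops at Visit 1 and that the site does not act on the other passages. About 145 patients are to be screened. The documents do not say how many use long-acting bronchodilators, so the number affected cannot be given. The consequence is for patient cover and site consistency in screening, not for power or the primary analysis.

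**What to change.** The sponsor should reconcile Table 1 and footnote s, the synopsis, Sections 2.3, 4.1, 5.1 (inclusion 7) and 6.5 with Tables 5 and 6, and SAP 1.2, so that:

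1. the Table 1 dispensing row for each drug matches the period in which the text says it is used; and
2. one group is named everywhere for ipratropium between Visits 1 and 2.

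Which period and which group are intended is for the sponsor to decide. Tying both rows to patients who start a wash-out at Visit 1 would not by itself reconcile the text. Table 6 wash-outs also apply to drugs other than LAMAs and LABAs, such as leukotriene modifiers, and inclusion 7 links salbutamol to Visit 1 without reference to wash-out.

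The cost is a few table cells and one sentence in a protocol amendment, plus any change in when supplies reach sites. No added visits, patients or analyses are needed.
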